All POC UHCG results will be communicated with the attending provider (verbally and by being documented in the comments section of the T-System™ home screen) and the attending provider will be responsible for conveying the results to the female potential subject. In the event that the female potential subject is a patient of the PI during the PIs ED shift, the PI with the permission of the attending may also convey the results of the test.

Upon meeting all of the aforementioned criteria for enrollment, providing a signature on the Informed Consent Form and HIPAA Authorization Form, the potential subject will be considered enrolled as a subject for the study.

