#### Randomization and Study Subject Packet Creation

Fully enrolled subjects will be randomized based on a two block randomization generated by the website [www.graphpad.com](http://www.graphpad.com). Randomization will be created so there are two groups (two block randomization), one which will receive 15 mg of intramuscular ketorolac and one which will receive 60 mg of intramuscular ketorolac. Each group (block) will consist of 61 subjects per the power analysis described later in this document and will be assigned a Subject Study Number.

The Subject Study Number will be comprised of a "K" for ketorolac, "15" or "60" designating which dose of ketorolac will be administered and then a specific number reflecting their position within the randomization block (randomization block number). For instance, a Subject Study Number of "K15-30" would signify that this patient was randomized into the ketorolac 15 mg group and the number 30 would reflect both the block to which the patient was randomized and confirm that the patient is indeed in the 15 mg group. Using both "15" or "60" and the randomization block number acts as a checks and balance to ensure that the patient is randomized into the correct group, and that the subject receives the correct randomized dose. Based on the randomization block number it is possible to know into which group the subject was randomized, the dose of ketorolac which will be administered and the order of the patient in the overall randomization. Following randomization, Subject Study Packets will be prepared.

Subject Study Packets will be prepared prior to the data collection (prior to the screening process). These packets will be created using manila envelopes capable of containing all study documents and which can be sealed. The contents of the envelopes will include the (1.) Ketorolac Research Form, (2.) Informed Consent Form (which includes consent for a POC UHCG), (3.) HIPAA Authorization Form, (4.) pretreatment VAS form, and two post-treatment VAS forms. None of the documents utilized or created throughout the study will be entered in to the subjects EHR. The manila packet and all documents contained within it will be annotated with the Subject Study Number (as described above). A description of these forms is listed below.

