3. HIPAA Authorization Form: signature of this document authorizes investigators use of the subject's protected health information (PHI) and personally identifiable information (PII) responsibly, securely and only for the purposes of this study. PHI and PII will be explained in detail to the patient and all questions will be honored. Should the patient decline to sign this document, they will be excluded from the study.
  1. PHI: The only protected health information used for this study will be the (1.) chief complaint and (2.) vital signs. A review of systems (ROS) will be used for inclusion and exclusion purposes of this study, but the EHR will not be accessed for this information and this information will not be documented on any media. A detailed description of the ROS is provided later in this application.
  2. PII: The only PII used for this study will be the (1.) subject name, (2.) age (in years-not date of birth), (3.) medical record number (MRN) and (4.) gender.

4. VAS forms (pretreatment and post-treatment): these are single page forms with a 0-100 mm VAS. Four separate VAS forms will be included in the Subject Study Packet and will be used to assess the subject's pain prior to administration of ketorolac, and at the 30 and 60 minute intervals after ketorolac administration. A fourth form will be included in the event that the patient completes the VAS incorrectly. The subject in each instance and on separate forms, will be asked to mark a horizontal line on the 0-100 mm continuum indicating their pre-treatment level of pain and their pain level post-treatment at the 30 minute and 60 minute intervals. Three separate forms are utilized to control for response bias. The Subject Study Number will also be included on the document, but otherwise no other information will be contained on the VAS forms.

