Study participants whose randomized dosing regimens are rejected by the attending provider will be excluded from the study. Again, attending provider concurrence with the randomized ketorolac dosing utilized in this study will be documented on the Ketorolac Research Form and is reviewed in the inclusion and exclusion portion of this application.

Prior to administration of ketorolac, a review of systems (ROS) will be performed with each patient to ensure that the subject has no medical history or other acute medical problems which would meet exclusion criteria for this study. However, this information will not be documented on any forms and will not be accessed through the EHR. The ROS is an anatomic or physiologic systems based detailed

interview with the patient to discuss their overall health and to identify any other medical issues that may or may not be connected with the patient's reason for ED visit.

The ROS used for this study is located within this application and will be located in the appendix of the manuscript when this study is complete. The study investigators' ROS may be separate from the actual attending provider ROS. The attending provider will perform their own ROS based on standard medical history taking. However, the ROS performed by the investigators for the purpose of this study will be used to discover any other medical issue or issues which may meet inclusion or exclusion criteria. If deemed pertinent to patient care, information obtained by performing the investigator ROS will be communicated verbally to the attending provider, so that they are aware that the patient may require evaluation for medical issues beyond an acute MSK injury or pain.

Ketorolac will be prepared for IM injection by the nursing staff assigned to the patient once the following have taken place:

1. Study subject has granted consent
2. Pregnancy is excluded
3. Breast feeding is excluded
4. Inclusion criteria are met
5. None of the exclusion criteria are met
6. The ROS is complete
7. The attending provider agrees to the randomized dose and formally prescribes the randomized dose of ketorolac through the EHR
8. Ketorolac will then be prepared for IM injection by the nursing staff assigned to the patient

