1. We have outlined several specific criteria for women. First, all women will be required to provide a POC UHCG to ensure that they are not pregnant. Those that decline to or cannot provide a urine sample will be excluded. Additionally, women who are pregnant or breastfeeding will be excluded due to the pregnancy risk factor category C and because it is known that ketorolac crosses into breast milk. These criteria were developed to ensure that the risk of ketorolac administration to a pregnant or breast feeding subject is all but eliminated.
2. For all study subjects, there are exclusion criteria related to specific processes which are known to be exacerbated or caused by the use of ketorolac. These include known, unknown, or suspected allergy or hypersensitivity to NSAIDS, peptic ulcer disease, intestinal hemorrhage, renal or hepatic insufficiency, suspected or confirmed cerebrovascular bleeding, hemorrhagic diathesis, incomplete hemostasis, dark stools, bright red blood per rectum, hemoptysis, easy bruising, or high risk of bleeding. Additionally, potential subjects will be excluded if they have ever been advised by any medical provider to not receive non-steroidal anti-inflammatory drugs (NSAIDs) for any reason.
3. Due to the increased risk of adverse effects with higher doses of NSAIDS, patients will be excluded who have used over-the-counter or prescribed NSAID analgesic medication (oral, per

rectum, topical or parenteral) taken within 12 hours of ED presentation. This ensures that study subjects are not provided with NSAID doses above what is recommended.

4. Potential study subjects will be excluded who have any other medical concern identified either through patient history or through the review of systems. This criteria is set as it is the study's aim to evaluate the efficacy of intramuscular ketorolac for pain management, alone. It is not the intent of the investigators to withhold or prevent a complete evaluation and therapy for any medical condition identified during the study period.
5. Finally, potential subjects will be excluded who are unable to confidently convey or report unknown medical history. This prevents the administration of ketorolac in subjects with possible undiagnosed disease.

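### The protocol does not settle whether the review of systems precedes randomisation, and exclusions based on it, by investigators who can know the arm, could not be audited for cause

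*Protocol*

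**What the plan says.** **Enrolment and randomisation.** Protocol 10.1 (Definitions; Prescreening / Recruitment Process) and 13.4 make eligibility a condition of enrolment. Once the criteria are met and the consent and HIPAA forms are signed, "the potential subject will be considered enrolled as a subject for the study". Section 10.1 (Randomization and Study Subject Packet Creation) continues: "Fully enrolled subjects will be randomized based on a two block randomization".

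**Packets.** The same section has packets assembled before screening begins. The Subject Study Number contains 15 or 60 and appears on the envelope and on every form inside, including the consent form.

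**Review of systems.** Section 10.1 (Medication Administration) says: "Prior to administration of ketorolac, a review of systems (ROS) will be performed with each patient". Its stated purpose is to confirm that the subject has no condition meeting an exclusion criterion. In the list of conditions for preparing the injection, item 6 is "The ROS is complete", and item 7 is the attending's agreement to the randomised dose. On recording, the section says: "However, this information will not be documented on any forms and will not be accessed through the EHR". The HIPAA Authorization Form item repeats that "this information will not be documented on any media".

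**Exclusion rules.** Section 14.2, item 4, states: "Potential study subjects will be excluded who have any other medical concern identified either through patient history or through the review of systems". Section 12.6 has no matching entry.

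**Records of exclusion.** Section 13.6 provides for a separate record of withdrawals and exclusions that holds no PHI or PII. Section 10.1 says the Ketorolac Research Form documents the inclusion and exclusion criteria.

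**The concern.** Three features combine. The eligibility screen may fall after the arm is known. It can apply a rule that has no stated limit and is not in the formal criteria. Its findings are deliberately left unwritten. An investigator who can see that the packet says 15 or 60 could, without intending to, judge a borderline history differently in the two arms. The groups would then differ in who remains rather than only in dose.

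This route is separate from the attending's right to reject a dose. Here the study investigator decides, so repairing the attending step would leave it open. The SAP defines no analysis set, so it is also unstated how someone randomised but screened out before dosing would be counted.

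**Working it through.** **1. Timing, with the passages side by side**

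| Place in protocol | What it implies |
|---|---|
| 10.1 Definitions; Prescreening / Recruitment; 13.4 | All criteria are met before someone becomes a subject |
| 14.1 and 14.2 (introduction to the criteria) | At-risk patients are screened out during recruitment and consent |
| 14.2 item 4 | Speaks of potential subjects, the term for people not yet enrolled |
| 10.1 Randomization | Only fully enrolled subjects are randomised |
| 10.1 Medication Administration | The review is done on the subject before injection and is listed after consent and just before agreement to the randomised dose |

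The first four rows put the screen before randomisation, and the last points to after it. No sentence gives the order of the review and the allocation.

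**2. Knowledge of the arm**

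The packets, with the dose in their number, exist before screening. The worked example in Medication Administration has the PI randomise a patient to 15 mg and tell the attending. Section 9.4 calls the trial single-blinded, and no text conceals allocation from the investigator. The arm can therefore be known on either reading of the timing.

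**3. The plan's own sample size (11.5)**

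Inputs are margin 13 mm, SD 27 mm, true difference 0, one-sided alpha 0.05 and 80% power. With the noncentral t distribution, power is 79.98% at 54 per arm and 80.6% at 55, so the stated 55 is reproduced. The allowance is 55 × 0.10 = 5.5, rounded to 6, giving 61.

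**4. Losses unrelated to outcome**

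These cost only power. With 6 lost per arm, 61 − 6 = 55 remain and power is 80.6%. With 9 lost, 52 remain (78.6%). With 12 lost, 49 remain (76.5%).

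**5. Losses related to outcome, shift in the mean**

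Suppose k of the 61 in one arm are removed and their expected VAS change differs from the rest by δ. The arm mean moves by k × δ / 61. Both k and δ are assumed.

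- k = 4: 4 × 10 / 61 = 0.66 mm; 4 × 20 / 61 = 1.31 mm
- k = 6: 6 × 10 / 61 = 0.98 mm; 6 × 20 / 61 = 1.97 mm

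As a share of the margin, 0.66 / 13 = 5% and 1.97 / 13 = 15%.

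**6. Losses related to outcome, effect on the test**

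Suppose the k subjects are dropped from the 15 mg arm only, as those lowest on a baseline feature that correlates ρ with VAS change. With f = k / 61, bias = ρ × 27 × φ(z_f) / (1 − f), and SE = 27 × √(1/(61 − k) + 1/61). The type I error is the chance of declaring non-inferiority when the true deficit is exactly 13 mm. Both k and ρ are assumed.

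| k | Bias, ρ = 0.3 to 0.5 | One-sided type I error |
|---|---|---|
| 3 | 0.87 to 1.45 mm | 7.1% to 8.8% |
| 6 | 1.56 to 2.60 mm | 9.1% to 12.9% |
| 9 | 2.19 to 3.65 mm | 11.2% to 17.6% |

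With ρ = 0 the error stays at 5%.

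**The case against.** A reader might infer that exclusions here leave no trace. The documents do not support that. Section 13.6 requires exclusions to be recorded, the research form documents the criteria, and the master key lists each enrolled subject's number before dosing. Gaps in the pre-numbered packets should be countable by arm. What is unrecorded is the finding behind an exclusion.

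A reader might also infer that the review is definitely done after randomisation. That is not established either. Sections 14.1 and 14.2 place screening in recruitment and consent. The list in Medication Administration reads as a set of conditions to be satisfied. It also includes pregnancy exclusion and the inclusion and exclusion criteria, which other sections make conditions of enrolment. An item's position in that list does not prove the sequence.

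Finally, the illustrated shifts are modest. They assume a one-sided loss, and because the review precedes dosing, selection can act only through baseline features and never through observed response.

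All of this stands. It does not answer three points: the arm can be known when eligibility is judged, the open-ended rule is outside 12.6, and the exclusion log is not required to state arm, reason or timing relative to allocation. A count of missing packets by arm would show imbalance but could not show whether each exclusion was justified.

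**Conclusion.** The concern holds as one of conflicting timing and weak auditability. The passages on when the review of systems occurs must be reconciled. As written, they allow an investigator who knows the arm to exclude someone under a rule not in the formal list, with no record of the finding.

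The size is uncertain because the documents give no exclusion rate. Under the assumed losses of 4 to 6 of 61 in one arm and a 10 to 20 mm difference, the arm mean moves about 0.7 to 2.0 mm. Under the assumed correlations of 0.3 to 0.5, three to six selective losses from the 15 mg arm raise the 5% error to between 7.1% and 12.9%. If the losses are unrelated to outcome there is no bias. They then draw only on the six-per-arm allowance, which other withdrawals must share. The change should be made, since it is inexpensive and the plan offers no other protection at this step.

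**What to change.** - In Protocol 10.1, state one order: consent, pregnancy test, review of systems and all other eligibility checks are complete before a concealed allocation is revealed.
- Keep the consent and eligibility forms outside the dose-coded packet, or use numbers that do not show the dose. Moving the review earlier is not enough. The pregnancy test needs consent, the consent form now sits in a packet marked with the dose, and a visible next packet would allow the same selection.
- On the Ketorolac Research Form, record a de-identified yes/no for the review of systems and, for an exclusion, the criterion applied. Amend the two statements in 10.1 that forbid documentation.
- Require the record in 13.6 to give arm, reason and timing for any exclusion after allocation.
- Reconcile item 4 of 14.2 with 12.6 so that a single exclusion list applies. Its clinical content is for the investigators to settle.
- In the SAP, define the analysis set by randomisation and state how subjects randomised but not dosed are handled.

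The cost is a change to packet assembly and numbering, one or two form fields, and matching edits to the HIPAA wording. The review of systems is already part of the procedure, so patients face no added step.

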#### **14.3**

#### **Confidentiality Protections (for research records, data and/or specimens):**

Describe in detail the plan to maintain confidentiality of the research data, specimens, and records throughout the study and at its conclusion (e.g., destruction, long term storage, or banking). Explain the plan for securing the data (e.g., use of passwords, encryption, secure servers, firewalls, and other appropriate methods). If data will be shared electronically with other team members/collaborators outside the institution, describe the method of transmission and safeguards to maintain confidentiality. Explain whether this study may collect information that State or Federal law requires to be reported to other officials or ethically requires action, e.g., child or spouse abuse

Study subjects will not be identified by their name, social security number, or medical records number (MRN) for the production of the final manuscript, poster, or any publication of the findings of this research. The master key used to identify study subjects will be maintained by the investigator for the duration of the study then destroyed once all data has been transferred from the Ketorolac Research Forms to the excel worksheet. All reportable data will be de-identified and collected on the Ketorolac Research Form and the VAS forms. The documents will be held in a locked locker in the WBAMC ED for the duration of the data collection period, analysis period, and as the manuscript is produced. Upon completion of the manuscript, the documents will be securely transferred to the WBAMC room 10015 and secured in a locked cabinet for a period of up two years. Upon completion of the two-year post-study period, the documents will be destroyed in accordance with WBAMC sensitive document disposal policies.

All data used for analysis will be compiled using Microsoft Excel into a table for ease of reporting. This, password protected, electronic document will be created and stored on a U.S. government issued laptop authorized to create and hold PHI and PII. This laptop is individually issued to the PI, CPT [name], and he is the only person who will have access.

If information must be shared between the investigators or personnel involved in the study (such as statisticians or the WBAMC Department of Clinical Investigations) via encrypted email, only a DoD email address will be used (such as [contact] or [[contact]](mailto:[contact])). Study information will never be sent to a civilian email or any other email address. Also, only de-identified data will be sent via email and this will be protected by the U.S. Army and WBAMC firewalls, which in theory will prevent any breach of this information. Encryption will also be used to add another level of security to email correspondence.

Information for this study will never be posted or stored on any social media website, blog or online database (such as Google Drive, Google Documents, Dropbox, etc.). Any publication of this data or

presentations regarding study findings will proceed only after required approval by the WBAMC authorities governing such actions.

#### **14.4 Potential Benefits:**

Describe any real and potential benefits of the research to the subject and any potential benefits to a specific community or society

If the individuals in the research are considered experimental subjects (per 10 USC 980), and they cannot provide their own consent, the protocol must describe the intent to directly benefit all subjects

Ideally, this study will determine that lower doses of IM ketorolac, given in the emergency department for moderate pain, can achieve equal analgesia compared to high dose of IM ketorolac. We anticipate that there will be a lower rate of adverse outcomes by utilizing lower doses of ketorolac. These findings result in several benefits to the DoD service member and beneficiary. First, by showing a lower rate of adverse outcomes, treating with the lower dose may help improve readiness by decreasing lost man power time. Secondly, reducing the amount of adverse effects while maintaining the same level of therapy, patient satisfaction may improve, as well. Additionally, the outcomes of this study may be used to build a larger, multicenter study to create data which could be generalized to a larger, more complex group of individuals.

#### **14.5 Privacy for Subjects:**

Describe the measures to protect subject's privacy during recruitment, the consent process, and all research activities, etc.

During the recruitment phase, the subjects' name, MRN, and Subject Study Number will be annotated on the master key. The master key will be a paper document which will be maintained by the investigator for the duration of the study. It will be secured in a padlocked locker within the WBAMC ED for the duration of the study.

The recruitment phase will be initiated in the waiting room by requesting them to step off to a more private, secluded portion, where they will be given the verbal synopsis (enclosed) by the PI or AI. Within this secluded portion, an enclosed room, within the Emergency Department the potential subject will complete the pre-screening and consent processes.

During the consent process, the study subjects will fill-out, sign, and date Informed Consent Form and HIPAA Authorization Form. These forms, with PII, will be maintained and secured in the same manner as the master key. The Subject Study Packets, containing the Ketorolac Research Form and VAS forms, will contain PHI but no PII as these forms will be annotated with only the Subject Study Number and will be de-identified (no PII will be on these documents). However, these forms will be secured in the same manner as the other forms.

Upon completion of the data collection phase, all forms will be transferred securely to WBAMC room 10015 and secured in a locked cabinet or locker, behind a locked door (secured with a cypher lock) for a minimum of two years following the completion of this study, in accordance with IRB and WBAMC policies.

The single electronic document will be the Excel worksheet used to compile all study subject data. The document will be located on the PIs government issued laptop. This worksheet will be password protected and saved to the hard drive of the PIs laptop. The hard drive on the computer can only be accessed by the person who saved it and network system administrators. All measures have been created to protect the information of the study though there will not be any PHI or PII on the document. This document will be destroyed upon completion of the dissertation defense.

